- Subject is willing and able to maintain his or her current pre-study Lateral Epicondyle pain management regimen of pain relief medication and/or treatment/therapy use throughout the course of study duration, whilst refraining from consuming other OTC and/or prescription medication(s) and/or herbal supplements intended for the relief of pain and/or inflammation, including muscle relaxants, and/or partaking in other treatments/therapies including conventional therapies such as physical therapy, occupational therapy and hot or cold packs, as well as alternative therapies such as chiropractic care and acupuncture.
- 18 years of age or older
- Male or female
- Subject is fluent in Portuguese

EXCLUSION CRITERIA

A subject who satisfies any of the following criteria will be excluded from study participation:

- hemophilia or any type of blood clotting disorder
- chronic immune impairment neoplasia
- neurologic deficits
- cervical radiculopathy
- peripheral nerve disease
- rheumatoid arthritis
- shoulder disease
- radial tunnel syndrome
- previous surgery of the affected upper extremities
- congenital or acquired bony deformity in the ipsilateral upper extremity
- the initiation of opioid analgesia or corticosteroid or analgesic injection interventions within the previous 6 months

- physical therapy intervention on the upper extremity in the previous year
- bilateral epicondylitis
- secondary orthopedic problems.

Physical Examination of the Lateral Epicondyle Region:

- Lateral Epicondyle pain is acute, defined as having persisted over less than the last 1 month
- Self-reported Degree of Pain rating on the 0-100 VAS pain scale for the Lateral Epicondyle region is less than 50
- Local corticosteroids and/or botulinum toxin (Botox®) injection for Lateral Epicondyle pain relief within the prior 30 days
- Medical tx; such as chiropractic care and acupuncture within last 30 days
- Current, active chronic pain disease: chronic fatigue syndrome, fibromyalgia, endometriosis, inflammatory bowel disease, interstitial cystitis diabetic neuropathic pain
- Cancer or treatment for cancer in the past 6 months, including tumors of the spinal cord
- Diabetes Type 1
- Significant heart conditions including CHF and implantable heart devices such as a pacemaker
- Active infection, wound, or other external trauma to the areas to be treated with the laser
- Medical, physical, or other contraindications for, or sensitivity to, light therapy

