2) **Parametric ANCOVA model** analysis with the mean change from baseline to study endpoint in Lateral Epicondyle pain ratings on the VAS as the dependent variable, procedure group as the independent variable of interest and baseline average Lateral Epicondyle pain VAS rating as a covariate. A two-tailed significance level of 5% will be considered to be statistically significant.

Covariates: The following potential covariate baseline variables will be adjusted, as applicable, through application of an ANCOVA analysis for the continuous variables and linear regression analysis for categorical variables.

- Baseline Lateral Epicondyle pain VAS rating
- Fitzpatrick Skin Type Classification
- Age
- Gender
- Demographics

SUPPORTIVE OUTCOME MEASURES

The following supportive outcome measures will be evaluated:

- a. Mean and individual subject changes in Degree of Pain VAS ratings across and between all study evaluation time points, within and between procedure groups
- b. Mean and individual subject changes in each of the PRTEE, grip strength and TNFa levels measurements across and between all evaluation points, within and between procedure groups
- c. Differences in satisfaction with Study Outcome Ratings between procedure groups at both evaluated time points, and any change between

SUPPORTIVE MEASURES STATISTICAL EVALUATION METHODS

- a. Supportive measures that are continuous variables will be analyzed through parametric analysis using ANCOVA. A two-way significance level of 5% will be statistically significant.
- b. Supportive measures that are categorical will be evaluated through linear regression analysis.
- c. Satisfaction with Study Outcome Ratings: will be tabulated according to category and reported as percentages. Satisfaction levels will be correlated with subject individual study success and recorded changes in Lateral Epicondyle pain VAS ratings from baseline to endpoint evaluations.

STATISTICAL EVALUATION OF APPLICATION OF PAIN MANAGEMENT REGIMEN

The impact of pain management regimen use on the study outcome measure will be evaluated through application of the following analyses:

- a. **Fisher's exact test** to compare the proportion of subjects requiring use of his or her individualized pain management regimen between the test and the control groups.

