- b. **Parametric ANCOVA model** analysis with the mean change from baseline to study endpoint in Lateral Epicondyle pain ratings on the VAS as the dependent variable, procedure group as the independent variable of interest and average dosage/frequency of use any component of the individualized pain management regimen. A two-tailed significance level of 5% will be considered to be statistically significant.
- c. **T-test analysis** to compare the frequency of usage of the pain management regimen across study duration between treatment groups.

- d. **Linear regression analysis** to evaluate the impact of frequency of usage of the pain management regimen across study duration on the primary outcome measure between procedure groups
- e. **Log Rank statistics** to evaluate differences in the time to first use of the pain management regimen between test and placebo procedure groups

BLINDING EFFICACY EVALUATION

Statistical evaluation of blinding efficacy will be performed as follows:

- (i) The percentage of subjects who correctly perceived their procedure group assignment and the percentage of subjects who did not correctly perceive their procedure group assignment will be calculated.
- (ii) The percentage of times the administration investigators correctly perceived subjects' procedure group assignment and the percentage of times the assessment investigators did not correctly perceive subjects' procedure group assignment will be calculated.
- (iii) The percentage of times the assessment investigators correctly perceived subjects' procedure group assignment and the percentage of times the assessment investigators did not correctly perceive subjects' procedure group assignment will be calculated.
- (iv) The **Fischer's Exact categorical analysis technique** for comparison of proportion of successes (accurate procedure group assignment determination) and failures (inaccurate procedure group assignment determination) between subject groups will be performed for each of the subject, administration investigator and assessment investigator determinations.
 - Comparisons will be made to evaluate if the proportion of correctly guessed subject procedure group assignments is greater than the proportion of incorrectly guessed subject group assignments.
 - Comparison will be made for each of the groups of subjects, administration investigators and assessment investigators, within and between treatment groups.

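### The use-adjusted models (items b and d) do not give a clean device effect, and the log-rank test of first regimen use (item e) can have little power; supportive analyses only

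*Combined protocol and SAP*

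**What the plan says.** The section STATISTICAL EVALUATION OF APPLICATION OF PAIN MANAGEMENT REGIMEN lists five analyses.

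- Item a is a Fisher test to "compare the proportion of subjects requiring use of his or her individualized pain management regimen between the test and the control groups".
- Item b is an ANCOVA of VAS change with "procedure group as the independent variable of interest", plus "average dosage/frequency of use any component of the individualized pain management regimen", tested at a two-tailed 5% level.
- Item c is a t-test "to compare the frequency of usage of the pain management regimen across study duration between treatment groups".
- Item d is a linear regression "to evaluate the impact of frequency of usage of the pain management regimen across study duration on the primary outcome measure".
- Item e is a log-rank test "to evaluate differences in the time to first use of the pain management regimen between test and placebo procedure groups". It has no stated time origin, event definition or censoring rule.

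Four other places bear on these items. The inclusion criteria require a subject "willing and able to maintain his or her current pre-study Lateral Epicondyle pain management regimen". The Table of Subject Events places randomization at step 4 and the stabilization phase on the regimen at step 5, and then allows use as needed through the procedure and follow-up phases. The stabilization phase lasts one week in that table and in the section that introduces it, but two weeks in the sections on stabilization measures and on procedure-phase measures. VAS ratings must be taken at least four hours after any pain-relief dose.

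**The concern.** Regimen use during the study is a post-randomization variable. A subject whose elbow hurts less may take less medication, so use can be a consequence of the device. Conditioning on it changes what the group coefficient in b means. It is no longer the full difference caused by assignment, and it can also pick up bias from unmeasured severity that drives both use and pain. Item d uses the same on-study variable.

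Item e has a different weakness. The event is the first use of something many subjects already use. If the clock starts at randomization, a regular user has the event during stabilization, when neither arm has been exposed to a device. If it starts at the first procedure, frequent users have the event within a day or two, perhaps before any device effect has developed.

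At stake is how the trial answers a natural question about an adjunctive pain device: whether concomitant analgesia explains the VAS result. A reader of b could see a real effect shrink, or grow, for reasons unrelated to the device. A reader of e could take a null result as evidence of similar use.

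**Working it through.** The plan states no figure for these analyses, so there is nothing of its own to reproduce. The only design input taken from it is 25 evaluable subjects per arm (Rationale for sample size). Everything else below is assumed, because the documents give no VAS SD, no rates of use and no time course of effect.

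**Item b.** Let T be 1 for the active arm, U unmeasured severity (SD 1), M on-study use (within-arm SD 1) and Y the VAS change, where negative is better:

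- M = -aT + bU + noise. The device lowers use by a SD.
- Y = -15T - gM + cU + noise. The drug lowers VAS by g mm per SD of use. The within-arm SD is 20 mm apart from the drug term.

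The total effect of assignment is -15 + ga. Given T and M, the expected value of U is b(M + aT), so the group coefficient with M in the model is -15 + abc. The difference, adjusted minus total, is a(bc - g). It is zero if a = 0, positive (toward the null here) if bc > g, and negative if bc < g. Simulation at 25 per arm, 1,500 replicates per scenario, agrees with the formula to about 0.3 mm:

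| a | b | c | g | Total effect (mm) | Adjusted, formula (mm) | Adjusted, simulated (mm) | Power without / with use term |
|---|---|---|---|---|---|---|---|
| 0 | 0.7 | 14 | 0 | -15 | -15 | -14.99 | 0.74 / 0.84 |
| 0.5 | 0.5 | 10 | 0 | -15 | -12.5 | -12.81 | 0.74 / 0.59 |
| 1 | 0.7 | 14 | 0 | -15 | -5.2 | -5.20 | 0.74 / 0.15 |
| 1 | 0 | 0 | 5 | -10 | -15 | -15.31 | 0.38 / 0.63 |
| 1 | 0.5 | 10 | 5 | -10 | -10 | -9.94 | 0.42 / 0.34 |

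The rows show no bias, attenuation, exaggeration and cancellation. Without the use term, the model recovers the total effect each time.

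**Item e, clock at randomization.** With a daily use probability p, independent across days, the share of subjects whose first use falls within a stabilization phase of d days is 1 - (1 - p)^d.

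- p = 0.3: 1 - 0.7^7 = 0.92 for one week; 1 - 0.7^14 = 0.99 for two.
- p = 0.1: 1 - 0.9^7 = 0.52 for one week; 1 - 0.9^14 = 0.77 for two.

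Those events cannot reflect the device.

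**Item e, clock at the first procedure.** With 21 days, 25 per arm and daily use halved in the active arm, either from day 1 or from day 8, power is:

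| Placebo daily use | Log-rank, day 1 | Log-rank, day 8 | t-test on days of use, day 1 | t-test on days of use, day 8 |
|---|---|---|---|---|
| 0.9 | 0.99 | 0.05 | 1.00 | 1.00 |
| 0.3 | 0.74 | 0.05 | 1.00 | 0.97 |
| 0.1 | 0.62 | 0.15 | 0.88 | 0.51 |
| 0.05 | 0.45 | 0.14 | 0.54 | 0.25 |

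The t-test figures are optimistic, because every subject in an arm is given the same daily probability. In practice subjects will differ in habitual use, which is a reason to adjust for stabilization-phase use.

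**The case against.** The strongest reply is that both harms are conditional. Subjects are told to keep their regimen as it was in stabilization. If they do, the device does not change use and item b is unbiased. The four-hour rule also limits any direct drug effect on the VAS. Item e is informative if use is infrequent at the start or the effect is immediate. The criterion on past relief from medication applies only where applicable, and item a's wording allows for non-users. The two criticisms also lean on different readings: a fixed regimen weakens the first, and both hold together most clearly for frequent as-needed use with a delayed effect. Appendix C, which holds the regimen details, is not in the text reviewed. All of this stands, and the point is worded accordingly.

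A reader might infer three stronger things that the documents do not support.

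- That these items are the plan's only check on concomitant analgesia. Items a and c compare use directly between arms and are untouched by this criticism.
- That the attenuation in b can be put at a definite figure. One could generate use from improvement itself, with a true effect of 12 mm, improvement variance 15² + 8² = 289, use variance 1.5² = 2.25 and slope k. The adjusted effect, ignoring the floor of use at zero, is then 12 × 2.25/(289k² + 2.25). That gives 10.8, 8.2 and 5.3 mm for k = 0.03, 0.06 and 0.10, a loss of 10% to 56%. The range only reflects the k chosen, and the model excludes both unchanged use and a drug effect.
- That item b omits baseline VAS. Its sentence is incomplete, and the general covariate paragraph lists baseline VAS for adjustment as applicable, so omission is not established.

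It can also be said that a model with only pre-exposure covariates comes close to the primary ANCOVA and no longer addresses on-study analgesia. That is fair. The better answer to that question is the between-arm comparison of use: for extra analgesia to explain a benefit, the active arm would need to have used more of it.

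**Conclusion.** The point holds in a limited form. The group coefficient in b does not estimate the total device effect if the device changes use, and d rests on the same on-study variable. Under the assumed inputs the distortion runs from none, to about 10 mm toward the null (-5.2 against -15), to 5 mm away from it (-15 against -10). The documents do not fix its size or direction.

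Item e, a test of "time to first use of the pain management regimen", has no defined clock. Its power runs from 0.05 to 0.99 under the scenarios tried. It is poor where use is frequent and the effect delayed, and most first uses precede exposure if the clock starts at randomization and use is regular.

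The primary Fisher test and primary ANCOVA contain no on-study medication term, and the study success criteria do not depend on this block. Nothing here puts the primary result in doubt. This is a low-severity improvement to supportive analyses.

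**What to change.** 1. Replace the log-rank test in e and the unadjusted t-test in c with one ANCOVA of on-study frequency of use on procedure group, adjusted for stabilization-phase use from the daily diary. That use is recorded after randomization but before device exposure, so the device cannot have affected it. State the window for on-study use, starting at the first procedure, and report the difference with its confidence interval.
2. For the device effect in b, name baseline VAS and stabilization-phase use as the covariates. If the models in b and d with on-study use are kept, label them exploratory associations and state that their group terms are not interpreted as device effects.
3. Reconcile the one-week and two-week descriptions of the stabilization phase, so that the window for baseline use is defined.

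Item a can stay as it is. The cost is SAP wording and a little analysis work; the diary already covers the stabilization and procedure phases.

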TABLE OF SUBJECT EVENTS

The following table provides a progressive summary of subject events throughout this study.

PRE-PROCEDURE ACTIVITIES	
1. A potentially well-suited and interested candidate for participation in the study attends the investigator's office.	
2. The investigator reviews the informed consent form with the candidate.	
3. If the candidate continues to be interested and voluntarily signs the informed consent form, the study qualification evaluation phase of the study is performed.	
4. A qualified subject is randomly assigned to procedure group.	
5. One-week individualized pain management regimen stabilization phase occurs	
6. The following measures are recorded during the Stabilization Phase: 
▪ Subject Daily Diary▪ Degree of Pain Ratings on final three days	
PRE-PROCEDURE ASSESSMENT PHASE	
CONTINUED STUDY ELIGIBILITY EVALUATION	

▪ Review of application of individualized pain management regimen throughout the Stabilization Phase▪ Evaluation of 3-day average VAS rating	
PRE-PROCEDURE MEASURES	

▪ Degree of Pain Rating▪ PRTEE, Grip Strength and TNFa measurements	
PRE-PROCEDURE VARIABLES	

▪ Baseline concomitant medication and treatment/therapy use	

- Historical pain medication and treatment/therapy use
- Baseline Lateral Epicondylitis pain variables
- Demographics

PROCEDURE ADMINISTRATION PHASE

Six 9-minute study procedure administrations with the Multi Radiance Medical® Prototype Device, two procedure administrations a week for three consecutive weeks administered at the test site.

PROCEDURE ADMINISTRATION PHASE MEASURES

DAILY THROUGHOUT THE THREE-WEEK PROCEDURE ADMINISTRATION PHASE

- Maintenance of the individualized pain management regimen, as needed
- Subject Daily Diary

WITHIN 24 HOURS OF COMPLETION OF THE FINAL PROCEDURE ADMINISTRATION

- Degree of Pain Rating
- PRTEE, Grip Strength and TNFa measurements
- Subject Satisfaction with Overall Outcome Rating
- Perceived Group Assignment
- Investigator Adverse Events Evaluation

POST-PROCEDURE ADMINISTRATION PHASE

DAILY THROUGHOUT THE ONE MONTH POST-PROCEDURE ADMINISTRATION PHASE

- Maintenance of the individualized pain management regimen, as needed
- Subject Daily Diary

ONE MONTH (30 DAYS) POST-PROCEDURE ADMINISTRATION PHASE (TEST SITE VISIT)

- Degree of Pain Rating
- PRTEE, Grip Strength and TNFa measurements

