- Pregnant, breast feeding, or planning pregnancy prior to the end of study participation
- Serious mental health illness such as dementia or schizophrenia; psychiatric hospitalization in past two years
- Developmental disability or cognitive impairment that in the opinion of the investigator would preclude adequate comprehension of the informed consent form and/or ability to record the necessary study measurements
- Involvement in litigation and/or receiving disability benefits related in any way to the parameters of the study
- Subject is less than 18 years of age
- Participation in a clinical study or other type of research in the past 30 days
- Subject is not fluent in Portuguese

SUBJECT GROUP RANDOMIZATION

A fully qualified subject is randomly assigned to 'Test Group A' or 'B' following the methodology outlined above in the STUDY DESIGN section of the protocol.

INDIVIDUALIZED PAIN MANAGEMENT REGIMEN STABILIZATION PHASE:

During the one-week period immediately preceding commencement of the pre-procedure assessment phase, subjects will partake in a pain management stabilization phase. See **Appendix C** for Individualized Pain Medication Regimen Details.

ESTABLISHMENT OF PROCEDURE ADMINISTRATION VISIT SCHEDULE

To implement consistency in the time of day when VAS pain ratings are recorded across all evaluation points throughout the study duration, the visit schedule times for each of the six procedure administration visits will be established at this time within a one-hour time frame. For example, between 2 p.m. and 3 p.m. for each of the six procedure administration visits, or between 10 a.m. and 11 a.m. for each of the six procedure administration visits, etc.

INDIVIDUALIZED PAIN MANAGEMENT REGIMEN STABILIZATION PHASE MEASURES

During the two-week stabilization phase, the subject records the following, as applicable.

- Subject Daily Diary
- Degree of Pain Rating on the 0-100 VAS on each of the last three days of the baseline stabilization phase, each measurement to be recorded within 15 minutes of the procedure administration visit times scheduled. For example, if the procedure administration visit schedule is established as between 2 p.m. and 3 p.m., the latest time a required VAS recording can be made is 3:15 p.m. The subject will record the exact time that he or she marks the VAS recording.

PRE-PROCEDURE ASSESSMENT PHASE

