Daily throughout the one-week post-procedure administration phase, the subject will continue at home to:

- maintain application of his or her individualized pain management regimen, as during the two-week stabilization phase and the three-week procedure and phase, and
- complete the Subject Daily Diary, as applicable

ONE MONTH POST-PROCEDURE ADMINISTRATION PHASE (TEST SITE VISIT)

- Degree of Pain Rating: This time will be within the same one-hour time-frame as the prior post-procedure administration phase VAS ratings were recorded, 1 month after the final procedure administration; e.g., if the prior 3 post-procedure administration VAS recordings were made between 1:30 p.m. and 2:30 p.m. on each of the three days, then the 1 week post-procedure VAS recording will also be made between 1:30 p.m. and 2:30 p.m. The exact time the VAS rating is recorded will be noted.
- PRTEE, Grip Strength and TNFa measurements will be noted.
- Subject Satisfaction with Overall Outcome Rating
- Perceived Group Assignment
- Investigator Adverse Events Evaluation

ADVERSE EVENTS

At each evaluation and measurement point throughout the clinical study, and at any other time throughout the duration of the clinical trial that is necessary, any and all potential adverse events reported by a subject or observed by an investigator will be recorded on the case report form, and subsequently evaluated by the investigator for its relation to the study procedure and whether or not any corrective action needs to be taken. All potential adverse events recorded will be appropriately reported to the governing IRB, as applicable.

It is unlikely and not expected that any adverse events will result from implementation of this clinical study protocol. Prior clinical trials using low level laser light have not typically yielded any adverse events or reactions. However, potential adverse events that may feasibly occur from application of the Multi Radiance Medical® MR5® Prototype Device include, but are not necessarily limited to; skin irritation, discoloring, rash, indentations and infection.

PRIVACY AND CONFIDENTIALITY

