CHANGE IN SUBJECT SELF-REPORTED VAS PAIN RATING FROM BASELINE TO STUDY ENDPOINT

Primary efficacy outcome measure for this clinical study will be a statistically significant difference in the proportion of subjects between test and control groups who achieve a clinically meaningful and statistically significant decrease in self-reported VAS pain rating from baseline to study endpoint.

Subjects meeting Individual Success Criteria

The individual subject success criteria is defined as a 30% or greater decrease in self-reported VAS pain rating at study endpoint relative to baseline.

Overall Study Success Criteria.

Overall study success criteria is defined as at least a 30% difference between procedure groups, comparing the proportion of individual successes in each group. It is anticipated that about 50% of subjects in the test group will meet the individual success criteria and about 20% of subjects in the control group will meet the individual success criteria.

Evaluation Time Points

The study end evaluation time point at which study success will be analyzed is within 24 hours following completion of the three-week procedure administration phase with the Multi Radiance Medical® MR5® Prototype Device. Study success will be evaluated at endpoint relative to baseline.

Hypotheses

- *Null Hypothesis:* There will be no statistically significant difference in the proportion of individual successes, as defined, between the test and control groups.

- *Alternative Hypothesis:* There will be a statistically significant difference in the proportion of individual successes, as defined, between the test and control groups, to the effect of 30% or greater.

PRIMARY EFFICACY OUTCOME STATISTICAL EVALUATION METHODS

Intent to Treat (ITT) Principle: Primary efficacy analysis will be according to the intent to treat (ITT) principle; wherein subjects will be included in the analysis if they were randomized to study procedure group, had a valid baseline (pre-procedure) visit including the required Lateral Epicondylitis pain VAS recordings; and received at least the first study procedure administration.

Missing data will be handled through all of the following methods:

- *Last Observation Carried Forward (LOCF):* by carrying forward the last recorded observation to fill in the subsequent missing value.

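### Regimen-use analysis d, and possibly b, can treat medication use recorded after the 24-hour endpoint as an influence on that endpoint; both need a window that stops at the endpoint VAS

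*Combined protocol and SAP*

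**What the plan says.** The section on statistical evaluation of the pain management regimen opens with a single purpose: "The impact of pain management regimen use on the study outcome measure will be evaluated through application of the following analyses". Three of its five analyses matter here.

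- Analysis d is a linear regression "to evaluate the impact of frequency of usage of the pain management regimen across study duration on the primary outcome measure between procedure groups".
- Analysis b is an ANCOVA of VAS change from baseline to study endpoint, with procedure group and "average dosage/frequency of use any component of the individualized pain management regimen" as predictors. It gives no period for that average.
- Analysis c is a t-test "to compare the frequency of usage of the pain management regimen across study duration between treatment groups".

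Under Evaluation Time Points, the time at which study "success will be analyzed is within 24 hours following completion of the three-week procedure administration phase" is fixed. Regimen and diary continue beyond it. The Table of Subject Events lists both "DAILY THROUGHOUT THE ONE MONTH POST-PROCEDURE ADMINISTRATION PHASE". The section on post-procedure evaluation points and measures has a shorter period: "Daily throughout the one-week post-procedure administration phase, the subject will continue at home to" follow the regimen and fill in the diary.

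The term *study duration* is never defined for a subject. The Study Duration section gives only four to five months for the trial as a whole. The inclusion criteria require the pre-study regimen to be held for the whole of it. The visit-schedule section asks for consistency in the time of day when "VAS pain ratings are recorded across all evaluation points throughout the study duration", and a VAS rating is due at the one-month visit.

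**The concern.** An analysis of the impact of medication use on an outcome should count only use that came before the outcome. If the diary is summed over all of a subject's participation, the exposure in d includes days after the endpoint was recorded. Subjects still in pain are likely to take more afterwards, and those who responded to take less. The regression would then pick up an effect of the outcome on use and label it an impact of use on the outcome. Analysis b has the same exposure to this error if its average is taken over the whole diary.

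At stake is the interpretation of the section, not the success of the trial. The claim sought is adjunctive use, so whether background medication explains the result is a question a regulator may well ask. An unspecified window also leaves several versions of b and d to choose from after the data are seen.

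**Working it through.** The plan states no figure on this point, so there is none to reproduce. The check is a timeline followed by illustrations.

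**Inputs from the document**

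- Stabilization phase: 7 days (Table of Subject Events) or 14 days (stabilization-phase measures).
- Procedure phase: three weeks, 21 days.
- Diary after the endpoint: 7 days (post-procedure phase text) or 30 days (Table of Subject Events).
- 30 subjects per arm; anticipated success 50% v 20% (sample-size rationale).

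**Share of diary days after the endpoint** = post / (stabilization + procedure + post)

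| Stabilization | Post 7 days | Post 30 days |
|---|---|---|
| 7 days | 7/35 = 20% | 30/58 = 52% |
| 14 days | 7/42 = 17% | 30/65 = 46% |
| not counted | 7/28 = 25% | 30/51 = 59% |

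**Illustration for d.** Assumed: subject dose rates follow a gamma distribution with mean 7 a week and between-subject coefficient of variation (CV) 0.5 or 1.0; counts are Poisson; there is one stabilization week; use before the endpoint has no effect on success; successes cut their use after the endpoint by 50% or 25%. Success is regressed on group and use. Over 20,000 trials, the use term is rejected at the 5% level as follows:

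| Cut after success | CV | 7-day diary | 30-day diary |
|---|---|---|---|
| 50% | 0.5 | 9.3% | 45.0% |
| 50% | 1.0 | 5.2% | 12.8% |
| 25% | 0.5 | 5.7% | 13.1% |
| 25% | 1.0 | 4.8% | 5.9% |

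With use limited to the procedure phase, the same runs reject in 4.6% to 5.1%.

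**A harsher illustration.** Assumed: 50 subjects, a continuous outcome, 28 pre-endpoint days with the same 40% daily probability of use for everyone, and post-endpoint use driven by endpoint pain (log-odds 0.5 per SD). Regression on pre-endpoint use rejects in 4.7%. Regression on whole-duration use rejects in 48% (7 days) and 100% (30 days). With no lasting differences in use between subjects there is little to mask the reverse association, so this shows direction and not a likely size.

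**Does the window cure d?** Only in part. If successes halve their use from the middle of the procedure phase onward, the 21-day window itself rejects in about 38% (CV 0.5) or 11% to 12% (CV 1.0). The whole window then rejects in 41% (7-day) or 76% (30-day) at CV 0.5, and 12% or 22% at CV 1.0.

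**Effect on the device estimate.** In the first illustration with the 50% cut, the mean adjusted group difference is 0.284 to 0.300 against a true 0.300.

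**The case against.** The best counter-argument is that the window is undefined rather than wrong. Evaluation Time Points labels the 24-hour assessment as the end-of-study evaluation, so *study duration* could be read as stopping there. The visit-schedule sentence is weaker support than it looks, because it goes on to fix times for the six procedure visits only. This stands to the extent that an endpoint-limited reading cannot be excluded. But the plan does not state it, the inclusion criteria apply the term to the whole period of holding the regimen, and that period runs past the endpoint.

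Second, the outcome in d might be the VAS itself, which is also rated at one month. Relating use over the study to VAS over the study would much reduce the time-order problem. The statistical section, however, defines the primary efficacy measure as baseline to study endpoint, so the 24-hour outcome is the more natural target. The rejection rates for the binary responder apply only to that reading.

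Third, the illustrations rest on assumed dose rates, variability and behaviour, and several results are close to 5%. Subjects are also told to maintain the regimen as in stabilization, which may limit later change, although the Table of Subject Events adds that use is as needed. This stands.

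A reader might also infer that analysis c is wrong. It is not: it compares use between arms, and whole-study use is a legitimate quantity. If active use is 40% lower in the procedure phase only, power at CV 0.5 falls from 93% to 49% (7-day) or 20% (30-day). That assumes the effect on use stops when treatment does; if it persists, the figures are 78% and 88%. Part of the loss also comes from counting the stabilization week.

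**Conclusion.** The concern holds for d, and for b if its average runs past the endpoint. On the natural reading, about 17% to 52% of the diary days counted, stabilization included, come after the outcome that d sets out to explain. That can produce a spurious impact of use. How large it is depends on assumed behaviour after the endpoint: in the main illustration the distortion is small with a one-week diary and material mainly if the diary runs one month and between-subject variation in use is moderate.

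Two stronger conclusions are not supported. A reader might infer that the efficacy result is compromised, but no success criterion or primary test depends on b or d, the Fisher comparison is untouched, and the device effect adjusted in d hardly moves. A reader might also infer that a corrected window turns d into a valid estimate of the effect of medication. It does not: use before the endpoint is also post-randomization and can respond to pain. Severity is minor.

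**What to change.** In the regimen-use section, give b and d one window, for example:

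> Regimen use in analyses b and d is counted from the first procedure administration up to the recording of the endpoint VAS rating. Use after that rating is summarised by group and enters neither model. Both analyses are descriptive.

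Keep whole-study use in c and add a comparison limited to the procedure phase. While editing, settle whether the post-procedure diary lasts one week or one month, since that determines what the descriptive summary covers.

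The cost is SAP wording and one added comparison. No visit, data item or subject is needed, because subjects already record all medication throughout participation. The downside is a noisier estimate of use, from about 21 days instead of 35 (7+21+7) to 65 (14+21+30). The window should be fixed before unblinding.
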